BIOMEDICAL RESEARCH PROTOCOL

UNIVERSITY OF MISSOURI

Project Title: The Use of Intranasal Calcitonin to Improve Pain and Activity in Elderly Pelvic Ring Injuries

IRB Number: 2013172

Version Number: 2

Version Date: 09/13/2019

Principal Investigator: [name]

Funding Source: AOTNA Grant

I. Research Objectives/Background

1. Include primary, secondary, and exploratory objectives.

Primary Objective: To compare acute pain over a three-month period in geriatric patients with pelvic ring injuries who receive intranasal salmon calcitonin with those who do not receive intranasal salmon calcitonin

Secondary Objective: To compare function and activity over a three-month period in geriatric patients with pelvic ring injuries who are treated nonoperatively and receive intranasal salmon calcitonin with those who do not receive intranasal salmon calcitonin.

Exploratory objective: To compare radiographic healing in geriatric patients with pelvic ring injuries who receive intranasal salmon calcitonin with those who do not receive intranasal salmon calcitonin

2. Include background and rationale for initiating the study. Includes pre-clinical and clinical data, current experiences with procedures, drug, or device, and any other relevant information to justify the research.

It is anticipated that geriatric patients who sustain pelvic ring injuries and are treated nonoperatively will demonstrate decreased pain scores and improved subjective and objective function if they are started on intranasal salmon calcitonin within 5 days of injury compared to patients who do not receive intranasal salmon calcitonin. It is anticipated the decreased pain and improved activity/function will prevent complications associated with extended periods of bedrest.

II. Drugs/Biologics/Devices

1. Include the product, dose, route, and regimen.

200 IU of ISC(intranasal salmon calcitonin) daily for three months

2. Include the rationale for choosing the drug/biologic and dose, or for choosing the device to be used.

Intranasal salmon calcitonin (ISC) has been demonstrated to decrease pain and improve the level of activity in patients with acute vertebral osteoporotic compression fractures when administered within the first 5 days of onset of pain/injury. Recently, randomized

clinical trials have demonstrated calcitonin to be superior to NSAIDS in promoting early ambulation and preventing functional deterioration in patients with acute osteoporotic vertebral compression fractures.

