3. Describe restrictions on participation and appropriate screening procedures to ensure that the restrictions are maintained, including pregnancy testing.

- All patients meeting inclusion criteria will be screened by study personnel.

VI. Number of Subjects

1. Include anticipated enrollment number in this study. Include a break-down in numbers if there is more than one subject population.
 - 60 patients; 25 each group; 10 screen fails
2. Include statistical analysis or other justification for the number of subjects enrolled.

VII. Study Procedures/ Design/Treatment Plan

1. Include study procedures/design/plan; include the sequence and timing of study procedures (distinguish research procedures from those that are part of routine care). Include study duration and number of study visits required.
After obtaining informed consent, the following will be obtained:

Baseline: Treatment group will be prescribed 200IU of ISC daily for a period of 3 months. The control group will not be prescribed calcitonin. Participants will complete research only Iowa pelvis score questionnaire, SF-36 questionnaire and visual analogue scale (VAS) to assess subjective pain and function. Two-week follow up visit post discharge: participants will complete Iowa pelvis score questionnaire, SF-36 questionnaire and VAS to assess subjective pain and function. Participants will be referred for a standard of care DEXA bone density scan if they have no previous diagnosis of osteoporosis and no history of previous scan within a year. Six weeks post discharge: participants will complete Iowa pelvis score questionnaire, SF-36 questionnaire and VAS to assess subjective pain and function. Participants will undergo standard of care radiographic analysis of pelvic ring injury with AP/inlet and outlet pelvic x-rays 4. Twelve weeks post discharge: Participants will complete Iowa pelvis score questionnaire, SF-36 questionnaire and VAS to assess subjective pain and function. Participants will undergo standard of care radiographic analysis of pelvic ring injury with AP/inlet and outlet pelvic x-rays - Participants will perform a timed up and go (TUG) test.

2. Blinding, including justification for blinding or not blinding the trial. Describe un-blinding procedures.

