After informed consent is obtained, all patients who meet eligibility criteria will be randomized into one of two groups. Randomization will be achieved by numbering 50 sealed white envelopes (25 control, 25 treatment). There is no blinding to the randomization. It would be difficult to blind the participants, or the research personnel. We do not believe there will be any significant bias that can be corrected with blinding.

Treatment: 200IUof ISC daily for a period of 3 month

Control: Will not be prescribed calcitonin (ISC)

3. Justification of why participants will not receive routine care or will have current therapy stopped.
Patients will receive routine care during this study.
4. Definition of treatment failure or participant removal criteria.
Patients will be removed if they do not return to their follow-up visits or do not complete the study specific tasks.
5. Description of what happens to participants receiving therapy when study ends or if participation in the study ends prematurely.
Routine care will continue per the physician's standard of care treatment.
6. Include sub-studies or banking information (correlative/special studies)
None

VIII. Potential Risks/Adverse Events

1. Describe reasonably foreseeable risks or discomforts to the subjects and steps to minimize risks. This study is expected to have minimal risk to the patient since we are using the FDA approved dosage for this study. This risk will be minimized by going over the purpose of the study with the patient before obtaining consent, and allowing withdrawal from the study at any time.
2. Describe any stopping rules. Stopping rules would include any reactions or side effects to ISC or per the provider's discretion.
3. Include the plan for reporting unanticipated problems or deviations. This plan must include a five-day reporting requirement to the IRB once becoming aware of an event.

IX. Anticipated Benefits

1. Include both direct and indirect benefits for either the individual or society.
The benefit to society is to provide data that will eventually lead to decrease pain in patients with pelvic ring fractures by using intranasal Calcitonin within 5 days of injury.

No direct benefits will be promised. Subjects can expect to help add to public knowledge about the effect of pelvic rings fractures in elderly patients.

X. Compensation

1. Describe the amount, method, and timing of disbursement. Compensation can include checks, cash, gifts, extra/course credit, etc.

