Subjects will be paid \$10 for each visit they complete but will only receive one check once they finish their 12 week visit. Subjects will be paid \$30 at their final visit.

XI. Costs

1. Detail costs of study procedures, drugs, biologics, or devices and identify who will cover the cost. All costs are being covered by the AOTNA grant. No additional costs to the participants for being enrolled in the study. Participants will pay for all standard of care costs.

Cost:

\$1,800 – Calcitonin Costs (\$72 per participant x 25 participants)

\$1,500 – Participant Stipend (\$30 per participant x 50 participants)

\$6,500 – Study Coordinator (0.7 calendar months, 5.9% effort, of assistance, covering salary and benefits for this effort)

Total: \$9,800

XII. Data Safety Monitoring Plan

Describe the plan to monitor the data, if necessary. A plan is required for treatment and/or intervention studies, sensitive data are being collected, there is a possibility for subjects to experience adverse events, etc. Adverse events will be reported to the IRB as necessary within 5 days of becoming aware of the event.

1. The plan should include when something needs to be reported
2. The frequency of the monitoring, such as points in time or after a specific number of participants are enrolled
3. Who will conduct the monitoring, such as a data board, medical monitor, investigator, independent physician; the specific data to be monitored
4. Procedures for analysis and interpretation of the data
5. Actions to be taken upon specific events or end points
6. Procedures for communication from the data monitor to this site.

XIV. References/Appendices

1. Include findings from a literature search or pilot study must be outlined including appropriate detailed references to earlier studies and data.

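### Section VII.4 removes randomised patients for not returning or for an uncompleted study task without defining removal, so obtainable later scores can be given up

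*Protocol*

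**What the plan says.** Section VII.2 randomises patients after consent: "After informed consent is obtained, all patients who meet eligibility criteria will be randomized into one of two groups". The removal rule in VII.4 therefore falls on randomised patients: "Patients will be removed if they do not return to their follow-up visits or do not complete the study specific tasks". It has two triggers joined by *or*, with no threshold and no alternative way of collecting a score.

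Section VII.5, on what follows when participation ends early, says only: "Routine care will continue per the physician's standard of care treatment". Section VIII.1 allows withdrawal at any time but does not set withdrawal apart from removal.

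Under VII.1 the Iowa pelvis score, SF-36 and VAS are taken at baseline and at 2, 6 and 12 weeks after discharge, and the timed up and go test at week 12 only. At weeks 6 and 12, "Participants will undergo standard of care radiographic analysis of pelvic ring injury with AP/inlet and outlet pelvic x-rays". Section X pays $10 "for each visit they complete but will only receive one check once they finish their 12 week visit", and then gives $30 at the final visit.

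The primary objective (I.1) is "To compare acute pain over a three-month period in geriatric patients with pelvic ring injuries". Section VI plans 25 per group, and VII.2 says "There is no blinding to the randomization".

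**The concern.** A missed visit or a half-finished questionnaire is a gap in the data. Leaving the study is a different event. VII.4 joins the two under one undefined word, and nothing elsewhere keeps such a patient in follow-up. A coordinator who applies the sentence as written could stop approaching someone who would have given later scores.

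This is a rule of conduct that the protocol itself fixes. An SAP can decide which collected scores are analysed, but it cannot recover scores that nobody sought.

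It matters here because the objective spans three months, the trial has 25 per arm, and it is open label. In injured patients over 65, attending a visit or finishing a questionnaire plausibly depends on pain and function. Information is then lost and, if the dependence or the removal rate differs between arms, so is some comparability.

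**Working it through.** **Inputs from the protocol.** 25 per arm (VI); scores at baseline and weeks 2, 6 and 12 (VII.1); the removal rule (VII.4). The enrolment figure reproduces: 25 + 25 + 10 screen failures = 60. The protocol gives no SD, correlation, miss rate or link between missing and pain, so there is no planned precision to reproduce.

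**Assumptions, for illustration only.** VAS SD 25 mm; correlation 0.6 between any two visits; independent misses; no true effect; 5%, 10% or 15% undone or missed per visit. All collected scores, including baseline, enter a generalised least squares (GLS) fit with known covariance.

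**Two readings of the rule**
- *Task trigger only.* A questionnaire left undone at week 2 or 6, with the VAS done at that visit, leads to removal. Week-12 VAS retained: (1 − t)², against 100% without the rule. At t = 0.10 this is 0.9² = 81%.
- *Any missed visit.* Week-12 scores retained: (1 − q)³, against 1 − q without the rule. At q = 0.10 this is 0.729 against 0.90.

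**Scores lost at 10%, of 150 planned follow-up VAS scores (50 × 3)**
- Task trigger only: 50 × (0.10 + 0.19) = 14.5 with the rule, 0 without.
- Any missed visit: 150 − 50 × (0.9 + 0.81 + 0.729) = 28.0 with the rule, 150 × 0.10 = 15.0 without.

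**Standard errors.** With complete data:
- Week-12 difference: 25 × √(2/25) = 7.07 mm.
- Three-visit mean difference: 25 × √[(1 + 2 × 0.6)/3] × √(2/25) = 6.06 mm.

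With gaps, the information per arm is 25 × Σ pₖ Vₖ⁻¹, summed over the patterns k of observed visits, each Vₖ⁻¹ placed in the rows and columns of the visits seen. The variance of a difference is 2c′I⁻¹c. At 10%, the pattern shares with the rule are:
- Task trigger only: 0.10 seen to week 2, 0.09 to week 6, 0.81 to week 12.
- Any missed visit: 0.10 baseline only, 0.09 to week 2, 0.081 to week 6, 0.729 to week 12.

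Results in mm, with the rule v without it:

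| Per-visit rate | Three-visit mean, task only | Three-visit mean, any missed visit | Week 12, task only | Week 12, any missed visit |
|---|---|---|---|---|
| 5% | 6.10 v 6.06 | 6.18 v 6.09 | 7.27 v 7.07 | 7.40 v 7.17 |
| 10% | 6.15 v 6.06 | 6.33 v 6.13 | 7.50 v 7.07 | 7.77 v 7.27 |
| 15% | 6.21 v 6.06 | 6.50 v 6.18 | 7.75 v 7.07 | 8.22 v 7.39 |

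At 10% the three-visit standard error rises by 6.15/6.06 − 1 = 1.5% or 6.33/6.13 − 1 = 3.3%. The week-12 standard error rises by 7.50/7.07 − 1 = 6.1% or 7.77/7.27 − 1 = 6.9%.

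**Bias by simulation**, same model, week-12 difference, all collected scores used. Missing depends on same-visit pain with odds ratio 3 per SD in one arm only.
- Task trigger only: within 0.02 mm of zero.
- Any missed visit at 10%: 2.10 v 1.36 mm. With half the patients' misses fully linked across visits it is 1.69 v 1.48 mm. With all misses linked it is 1.43 v 1.66 mm, so the rule adds none.
- Equal dependence on pain in both arms: about zero.

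**The case against.** The strongest reply is that the sentence answers a template item and says less than it seems to. Several stronger inferences are tempting, and the protocol does not support them.

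- **That later scores will not be sought.** No passage says so. Removal could mean off treatment, out of the study or out of the analysis. What stands is that the word is undefined and nothing preserves follow-up.
- **That one missed visit triggers removal.** The wording is plural and reads more naturally as loss to follow-up, where little could be recovered. Payment per completed visit fits partial attendance, and $30 equals three follow-up visits at $10. This is suggestive, not proof. The larger figures rest on this less natural reading.
- **That removed patients leave the analysis.** The protocol does not say this and the SAP may settle it. Power losses computed as if removed patients vanished do not belong to this point.
- **That type I error is inflated to, or bounded by, a known value.** Any such figure depends on the assumed missingness model and on the analysis. None is claimed.

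The task trigger is also narrow. A task left undone at week 12, including the timed up and go test, costs no later score. Week 12 is not named as the primary time point, so the three-visit mean is the closer match to the objective, and there the loss is small. How often such patients could still be reached is not documented; the standard-of-care x-rays at weeks 6 and 12 only make contact plausible.

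These replies limit the size. They do not remove the point: on the milder reading, a patient who attends and leaves a questionnaire undone still meets the removal wording.

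**Conclusion.** The point holds as an undefined conduct rule that, taken literally, can forfeit obtainable later scores. The main cost is precision. Under the stated assumptions at 10% per visit, the standard error rises by about 1.5% to 3.3% for pain averaged over three months and by about 6% to 7% at week 12. Bias is conditional: it needs the removal rate, or its link with pain, to differ between arms. It is about zero on the task-only reading when all collected scores are used, and the rule may add none if the same patients miss every visit. Every rate, SD and correlation is assumed, so the sizes are illustrative. The change is worth making because it is cheap and the loss cannot be undone once visits have passed. Confidence is medium because the wording is ambiguous.

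**What to change.** Replace VII.4 with:

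> A missed visit or an uncompleted questionnaire or test does not remove a participant from the study. All randomised participants stay in follow-up through week 12 unless they withdraw consent or cannot be reached, and all remaining scheduled scores are sought.

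Missed questionnaires may be sought by mail or at the standard-of-care x-ray visits as coordinator time allows, with the VAS first. A telephone VAS is not part of this change, because it would alter the instrument.

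The cost is a one-paragraph amendment and some extra coordinator time, from a budget of 0.7 calendar months at 5.9% effort (section XI). No extra patients are needed and no treatment rule changes.

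### No visit asks about adverse events in either arm and the monitoring items are unanswered, so the stopping and reporting rules rest on events that happen to come to light

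*Protocol*

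**What the plan says.** Section VII.1 gives the content of each visit. At baseline: "Participants will complete research only Iowa pelvis score questionnaire, SF-36 questionnaire and visual analogue scale (VAS) to assess subjective pain and function". At two weeks: "Two-week follow up visit post discharge: participants will complete Iowa pelvis score questionnaire, SF-36 questionnaire and VAS to assess subjective pain and function", with a DEXA referral for some patients. At six weeks: "Six weeks post discharge: participants will complete Iowa pelvis score questionnaire, SF-36 questionnaire and VAS to assess subjective pain and function", with pelvic x-rays. Twelve weeks repeats the three questionnaires and x-rays and adds the timed up and go test.

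Two rules act on adverse events. Section VIII.2: "Stopping rules would include any reactions or side effects to ISC or per the provider's discretion". Section XII: "Adverse events will be reported to the IRB as necessary within 5 days of becoming aware of the event". The rest of XII is the form's own list of what a monitoring plan should contain, for example "The frequency of the monitoring, such as points in time or after a specific number of participants are enrolled", with no trial-specific answer beneath it.

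The trial is unblinded and the control arm receives no placebo (VII.2). Patients who do not return, or do not complete study tasks, are removed (VII.4). Section I.2 adds an expectation: "It is anticipated the decreased pain and improved activity/function will prevent complications associated with extended periods of bedrest".

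**The concern.** Both rules start once somebody on the team knows of an event, and no scheduled step produces that knowledge. The questionnaires are there for pain and function. Nothing at any visit asks about side effects, falls, readmission, conversion to surgery, complications of immobility or death.

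Two things are at stake. The first is patient safety: the stopping rule has no scheduled trigger during three months of daily drug in patients over 65. The second is the usefulness of the event data. Everybody knows the allocation, and the one event-based ground in VIII.2 refers to the study drug, so treated patients and their clinicians may be readier to mention or note an event than controls. If capture differs by arm, a comparison of counts partly measures capture. An analysis plan cannot repair this, because it can analyse only what was collected.

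**Working it through.** **1. The plan's own figure.** Section VI gives 25 per group plus 10 screen failures: 25 + 25 + 10 = 60, which reproduces. The protocol states no adverse-event rate and no expected number of events, so every rate below is an assumption.

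**2. Visit content, from VII.1.**

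| Visit | Listed content | Adverse-event enquiry |
|---|---|---|
| Baseline | Iowa pelvis score, SF-36, VAS; ISC prescribed in the treated arm | none |
| 2 weeks post discharge | same three; DEXA referral if applicable | none |
| 6 weeks | same three; x-rays | none |
| 12 weeks | same three; x-rays; TUG | none |

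The list is the same for both arms apart from the prescription. Set beside it, VIII.2 and XII each need an event to be known already. The items in XII on frequency, on who monitors and on which data would be the other place to create awareness, and they are blank.

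**3. Incomplete capture.** Let n = 25 per arm, p the true proportion of patients with an event, and s the share of those events that reach the team. Expected recorded events = n·p·s. Chance of recording at least one = 1 − (1 − p·s)^25.

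| True rate p | s = 1 | s = 0.75 | s = 0.5 | s = 0.3 |
|---|---|---|---|---|
| 4% | 1.0 event; 64% | 0.75; 53% | 0.5; 40% | 0.3; 26% |
| 10% | 2.5; 93% | 1.88; 86% | 1.25; 72% | 0.75; 53% |
| 20% | 5.0; 99.6% | 3.75; 98% | 2.5; 93% | 1.5; 79% |

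For example, p = 10% and s = 0.5 gives 1 − 0.95^25 = 0.72.

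**4. Unequal capture.** Apparent risk ratio = true risk ratio × (s treated / s control).

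- Equal capture, 50% and 50%: counts halve and the ratio is unchanged.
- 80% treated, 40% control: a true ratio of 1.0 appears as 1.0 × 0.8/0.4 = 2.0. A true 15% treated against 30% control gives 25 × 0.15 × 0.8 = 3.0 and 25 × 0.30 × 0.4 = 3.0 recorded events, so a halving of risk disappears.
- 40% treated, 80% control: a true ratio of 1.0 appears as 0.5.

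Equal capture therefore loses events without distorting the ratio. Distortion needs a difference between arms, and it can go either way.

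**5. What better collection cannot do.** With full capture and 30% against 15% (assumed), the expected counts are 7.5 and 3.75. Power at 25 per arm, two-sided 5%, normal approximation, is about 24%. Zero events in 25 excludes only rates above 1 − 0.05^(1/25) = 11.3% (one-sided 95%). Both limits come from the sample size and stay after the fix.

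**The case against.** The sentence in XII is not wrong. A reporting clock that starts at awareness is ordinary, and the form itself asks for it in VIII.3. That stands: the gap lies in VII.1 and in the unanswered items of XII, not in the clock.

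Routine care also continues for every patient (VII.3), and the x-rays at 6 and 12 weeks are standard of care. Clinicians may well learn of displacement, surgery or readmission. That also stands, so detection does not rest on spontaneous report alone. But the protocol does not say that what routine care reveals will be recorded, or recorded alike in both arms.

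Three stronger readings are tempting, and the documents do not support them.

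- A reader might infer that only the treated arm is watched. VIII.2 is a stopping rule, and side effects of ISC can arise only where ISC is given. Provider discretion and the reporting sentence in XII have no arm limit, and both arms share one visit schedule.
- A reader might infer that the minimal-risk statement in VIII.1 fails without these data. That statement rests on use of the approved dosage, not on events in this trial.
- A reader might infer that the trial sets out to test bedrest complications and then omits them. They appear in the rationale (I.2) only. The objectives are pain, function and activity, and radiographic healing.

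**Conclusion.** The point holds in limited form and should be acted on. Read as written, the protocol schedules no adverse-event enquiry in either arm and leaves its monitoring items unanswered. The rules in VIII.2 and XII therefore depend on events surfacing through spontaneous report or routine care. This follows from the text and needs no calculation. It is protocol content, so an unseen analysis plan does not excuse it.

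Incomplete capture is likely, given the schedule. A difference in capture between arms is possible, given open-label treatment without placebo and a stopping ground tied to ISC. Neither the size nor the direction can be read from the documents, and the capture shares and event rates in the working are illustrations. It would go too far to say that harms will be under-counted by a given amount, or that calcitonin will look falsely harmful or falsely safe.

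**What to change.** - Add to VII.1, at the existing 2-, 6- and 12-week visits, one identical short set of questions in both arms: new symptoms or side effects, falls, readmission, conversion to surgery, complications of immobility, and death, with onset date and severity.
- Continue event collection by phone or chart for patients who miss visits or would be removed under VII.4. Patients who have died, been readmitted or declined may be among those who do not attend, and a form used only at attended visits would miss them.
- Keep the 5-day clock running from first awareness. The visit form is one route to awareness and must not delay reporting of an event learned of between visits.
- Answer the open items in XII by reference to this form: which data, how often, and who reviews them.
- Report events by arm with denominators, descriptively, since 25 per arm cannot test complications.

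The cost is a few minutes per visit and more minor events recorded; no visit or procedure is added. Coordinator time is not free. Section XI funds 0.7 calendar months, which at an assumed 160 hours per month is 112 hours, or 112/50 = about 2.2 hours per participant. Three visits for 50 patients make 150 forms. At an assumed 5 to 10 minutes each, that is 12.5 to 25 hours, or 11% to 22% of the funded time, before any phone or chart follow-up. A one-page form keeps this near the lower end.
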